**Maximal aerobic power (VO2 max).** The measurement of VO2max (or peak) will be used to formulate the prescription for CEx at the screening visit. Increases in VO2max in response to exercise training will also verify that the exercise was of sufficient intensity to induce cardiorespiratory adaptations. During an initial 5-min warm-up, walking speed will be adjusted to elicit a HR that is ~70% of maximal HR (from the screening GXT). Speed will then be held constant and the grade of the treadmill will be increased by 2% every 2 minutes until volitional exhaustion or until the test is stopped (see section 4.1.2b). The O2 and CO2 content of expired air will be measured continuously by open circuit spirometry and averaged every 30 sec using an automated online system (TrueMax 2400; ParvoMedics, Sandy, UT). Objective evidence that VO2max has been attained will include at least 2 of the following: a plateau in VO2 despite an increased energy demand, a respiratory exchange ratio in excess of 1.10, and a maximal HR within 10 beats of the age-predicted value. In the absence of these benchmarks, the maximum measured VO2 will be deemed VO2 peak.

**Muscle strength (1-RM).** Muscle strength will be evaluated as the 1-RM (the maximal weight that can be lifted only 1 time using correct lifting form through the full range of motion) for the upper and lower body REx performed during weeks 1-16. 1RMs will be measured at week 0 and every 4 weeks to week 20. The change in muscle strength from week 0 to 16 will be a secondary outcome measure.

**Exercise Intervention.** Participants will be assigned with equal probability to one of the two exercise intervention arms (high intensity interval training [HIIT] or continuous moderate intensity exercise [CME]) following completion of screening procedures. Randomization procedures will be site-specific, and use permuted blocks with stratification by sex and 10-year age categories (i.e., 50-59 years, 60-69 years, 70-80 years), to assure similar distribution in each arm. The allocation to study arm will remain blinded (masked) to the research assistant conducting the physical function assessments and to laboratory personnel.

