## F. Data Analysis Plan:

**Statistical Considerations.** We hypothesize that among older PWH, HIIT will lead to better physical function and reduced fatigue through improvements in mitochondrial bioenergetics compared with CME.

**Sample Size Calculations:** We assume a 1:1 randomization to HIIT or CME balanced by site, sex ( $\geq 25\%$  women) and age category (50-59, 60-69, and 70+) with a conservative 20% dropout rate, resulting in 40 evaluable participants/group. The second randomization at week 16 and will also be balanced by initial randomization (2x2 factorial design). Aim 1 and 2 power calculations assume two-sided, 2-sample/paired *t*-tests for between/within group comparisons of the change from baseline with a 0.05 significance level. We assume conservative within subject correlations ( $\rho$ ) of 0.7 or 0.5 to estimate the standard deviation (SD) of the outcome change, larger correlations and repeated measures will result in additional power. The Aim 1 primary outcome is change in 400-MWT. We assume an effect size comparable to Toohey, an intervention comparing HIIT to CME among middle-aged (mean age 51, SD 12 years) cancer survivors that resulted in a mean (SD) difference of 97 (82) and 36 (68) meters in 6-minute walk distance among HIIT and CME, respectively. Using  $\rho=0.7$ , and a sample size of 40/group, we will have  $>88\%$  power to detect a comparable *between* group differences of 45 (38) and 20 (38) second improvement in 400-MWT in HIIT and CME, respectively. For reference, in our prior exercise study, PWH had a 25 second improvement in 400-MWT. This also provides  $>99\%$  and  $>81\%$  power to detect *within* group differences in the HIIT and CME arms. For morning and evening fatigue, we assume a baseline mean of 19(8) and 27(8) points, respectively ([name], unpublished data). With  $\rho=0.5$ , and a sample size of 40/group, we will have  $>80\%$  to detect a change of  $\geq 27\%$  and  $\geq 20\%$ , respectively. The primary Aim 2 outcome is change in State 3 respiration. Based on Robinson, we estimate a baseline mean (SD) of 580 (180) pmol  $O_2$ /min/mL using  $\rho=0.5$ . This provides  $>81\%$  power to detect a difference in the change of 50% (HIIT) and 30% (CME). The muscle substudy is considered exploratory, however, we anticipate adequate power. Using preliminary data, combining HEALTH+ exercise groups (N=24), provides  $>80\%$  power to detect a change of -8.7% in MRI-PDFF of HEALTH+ participants. For within exercise group (CME or HIIT) comparisons, a sample size of 12 provides  $>80\%$  power to detect a difference of -12.5%. For the CME versus HIIT change from baseline comparison, a sample size of 12 per group provides  $>80\%$  power to detect group differences of 9.8%. For the change in OxPhos, combining HEALTH+ exercise groups (N=24, 3 dropouts/group), provides  $>80\%$  power to detect an OxPhos change of 0.039. For within exercise group (CME or HIIT) comparisons, a sample size of 12 provides  $>80\%$  power to detect an OxPhos difference of 0.055. For the CME versus HIIT change from baseline comparison, a sample size of 12 per group provides  $>80\%$  power to detect group OxPhos differences of 0.056. For the change in aim 3, combining HEALTH+ exercise groups, a sample size of N=24 (3 dropouts/ group), provides  $>80\%$  power to detect a 21%  $\dot{V}O_2$  change in HEALTH+ participants. For within exercise group (CME or HIIT) comparisons, a sample size of 12 provides  $>80\%$  power to detect 33% change in  $\dot{V}O_2$ . For the CME versus HIIT change from baseline comparison, a sample size of 12 per group provides  $>80\%$  power to detect a 30% difference in the 16-week change from baseline.

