will examine potential group (and site) differences in demographics and health and baseline measures with two-sample t test (or Wilcoxon), ANOVA (or Kruskal-Wallis test) or Chi-square test where appropriate. Variables that differ by group will be adjusted in sensitivity analyses. We will conduct primary analyses under an intention-to-treat principle (all participants analyzed based on randomized conditions). The impact of any missing data will be mitigated by the use of mixed effects modeling with baseline covariates that are conceptually relevant and associated to consistency in data collection. In the presence of missing data, mixed effects models are fitted with all available data and provide unbiased estimates of model parameters, as long as the data are missing at random or conditionally at random (conditional on the covariates). If appropriate, we will employ imputation techniques. False discovery rate (FDR) will be used to justify multiple comparison. All tests will be two sided.

Our primary aim is to determine the efficacy of HIIT vs CME on improving cognitive function over time. In stage 1 (baseline to 4 months), a general linear mixed model with participant ID as random effect:  $\text{score} = \text{Group} + \text{Time} + \text{Group} \times \text{Time} + \text{Site}$  will be used first to examine whether there is a significant group difference, wherein the study site is controlled to adjust for potential site effects. The best model fit with Bayesian information criterion (BIC) will determine the variance-covariance structure in above model. The significant interaction term in above model indicates a significant difference between two trajectories/slopes, i.e., treatment effect. The group comparison on the mean changes will also be contrasted with t test for effect size. In stage 2 (4 to 7 months), a similar general linear mixed model will applied:  $\text{score} = \text{Group1 (HIIT vs CME)} + \text{Group2 (Coaching vs Control)} + \text{Group1} \times \text{Group2} + \text{Time} + \text{Group1} \times \text{Time} + \text{Group2} \times \text{Time} + \text{Group1} \times \text{Group2} \times \text{Time} + \text{Site}$ , where the time is from 4 to 7 months. The non-significant interaction terms will be removed from the final model. Given any potential group differences in demographics and health at baseline, a sensitivity analysis will be conducted including those unbalanced variables in above models.

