## STUDY TIMELINE

We propose a 5-year timeline to accomplish our specific aims (**Table 1**). By conducting a rigorous, prospective, randomized clinical trial testing two exercise regimens, we will overcome limitations of previous studies investigating non-pharmacological approaches to improving the *healthspan* of people living with HIV. This design enables us to characterize the clinical (i.e., physical function and patient-reported fatigue) and translational (i.e., mitochondrial bioenergetics) effects of these interventions in an understudied, yet growing, population. To ensure that we meet enrollment and data collection milestones, we anticipate 4.5 full years of research procedures, with the remaining 6 months to finalize data analyses and disseminate the final study results.

R01 Cognitive substudy (HEALTH-COG) will leverage newly enrolled participants at the two sites of the parent HEALTH study (R01AG066562), add a University of Alabama at Birmingham (UAB) site, add new measures (psychological mechanisms of adherence, cognitive function, biomarkers) and a 12 month follow-up. This study is optional (to UCD/UW participants) and open to anyone enrolled in the parent HEALTH study. The sub-study R01 proposes to enroll/randomize 110 participants (UAB=60, University of Washington (UW)/University of Colorado Denver (UCD)=50 total between the two sites). Based on current enrollment numbers at the parent study sites (UCD=37 and UW=31), we anticipate it will be feasible for the new R01 to enroll the remaining participants across both sites (~32 participants), and due to timing of funding in relation to enrollment at UCD and UW, approximately 8-10 additional participants at both UCD and UW will need to enroll to meet and overall goal of 110 in this sub-study. The parent study end date is ~2 years into new R01 (yielding 2-3 additional years of study).

| Table 1.               |     |                      |   |
|------------------------|-----|----------------------|---|
| Timing
(Year/Month) |     | Enrollment
Target | Milestones  |
| Year 1                 | JIT |                      | 
 
Protocol & Manual of procedures finalized
 
IRB approvals
 
Hospital/research center approvals
 
Data transfer agreements between UCD-AMC and UW finalized and executed
 
  |

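### The cognitive sensitivity analysis chooses its covariates by testing randomised groups for baseline differences; a fixed set, entered so that it can move the result, would be a better check at almost no cost.

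*Combined protocol and SAP*

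**What the plan says.** All of this stands in the Cognitive Substudy Statistical Analysis, under Analysis Plan, unless another section is named.

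- Baseline comparison: the analysts "will examine potential group (and site) differences in demographics and health and baseline measures with two-sample t test" and related tests, covering "baseline measures with two-sample t test (or Wilcoxon), ANOVA (or Kruskal-Wallis test) or Chi-square test where appropriate". No threshold is given beyond "All tests will be two sided".
- The rule: "Variables that differ by group will be adjusted in sensitivity analyses". It is repeated after the stage 1 and stage 2 models: "a sensitivity analysis will be conducted including those unbalanced variables in above models".
- Stage 1 model (baseline to 4 months): Group, Time, Group x Time and Site, with a participant random effect. The treatment effect is the Group x Time term.
- Stage 2 model (4 to 7 months): both randomised factors, their interactions with each other and with Time, and Site. Non-significant interactions are dropped from the final model.
- Multiplicity: false discovery rate control is mentioned, but not which tests it covers.
- Randomisation (section D, Exercise Intervention): "Participants will be assigned with equal probability to one of the two exercise intervention arms", site-specific, in permuted blocks stratified by sex and 10-year age category.

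No covariate is named for the sensitivity analysis.

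**The concern.** HIIT and CME are allocated at random, so a baseline difference between them is chance. A test of that difference carries no information on whether the variable predicts cognition. The rule can therefore bring in an irrelevant variable that happens to differ and leave out a strong predictor that happens to be balanced. The covariate set is known only after the arms have been compared, and it would change from one realisation of the trial to the next.

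What is at stake is how informative the covariate-adjusted check on the main cognitive comparison can be. The comparison itself is specified separately.

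**Working it through.** The documents give no power or precision figure for the cognitive comparison, so there is none to reproduce.

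**Inputs from the documents**
- Substudy size: "The sub-study R01 proposes to enroll/randomize 110 participants". Allocation is 1:1.
- Significance level: the parent power section (F, Sample Size Calculations) works "with a 0.05 significance level". Applying it to the baseline tests is an assumption.
- Within-subject correlation: the same section uses 0.7 or 0.5. I take 0.7 for the cognitive score, as an assumption.
- Dropout: 20% in the parent section, carried over as an assumption.

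**Assumed, with ranges:** 10 to 20 independent baseline variables, and R² of 0.1 to 0.5 between covariates and score. The score has SD 1.

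**1. Chance that something is selected.** For k independent tests at 5% the chance is 1 − 0.95^k.
- k = 10: 1 − 0.599 = 40%
- k = 15: 1 − 0.463 = 54%
- k = 20: 1 − 0.358 = 64%

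**2. Chance that a useful variable is selected.** If 3 of 10 variables are prognostic, at least one of the three is picked with probability 1 − 0.95³ = 14% (13.9% in simulation). Stratified factors have a lower chance still.

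**3. What a main-effect covariate does in stage 1.** With complete data the Group x Time estimate is the difference between arms in mean change. A baseline covariate entered as a main effect adds the same amount to a participant's score at both visits, so it cancels. The standard error is √[4 × 2(1 − 0.7)/110] = √(2.4/110) = 0.148. Fitting the plan's model to 150 simulated trials, with one covariate of R² 0.3, gave:

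| Dropout | Mean SE, no covariate | SE ratio with covariate | Mean absolute shift in estimate |
|---|---|---|---|
| 0% | 0.148 | 1.000 | about 5 × 10⁻¹⁶ |
| 20% | 0.162 | 0.994 | 0.014 |

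The result is the same however the covariate is chosen.

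**4. What a pre-specified set does if the model lets it act.** For a 4-month ANCOVA on the baseline score (N = 110, three prognostic covariates), the SE relative to ANCOVA without them was 1.00, 0.98 and 0.92 for R² of 0.1, 0.3 and 0.5. A covariate x Time term gave a ratio of 1.005 when the covariate did not predict change. It reduces the SE only if the covariate does predict change.

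**5. Stage 2 reduced to group main effects.** The analysed quantity is then each participant's average over the two visits. Its variance is 0.7 + 0.3/2 = 0.85, or 0.85 − 0.30 = 0.55 after a covariate with R² 0.3.
- Unadjusted SE: √(4 × 0.85/110) = 0.176
- Adjusted SE: √(4 × 0.55/110) = 0.141

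Simulation gave 0.176 and 0.143; the formula ignores the small cost of estimating the extra terms. Here a main effect does act.

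**6. Type I error.** In simulation with 46 per arm and one covariate, the adjust-if-different rule gave 4.5% to 5.0%.

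**The case against.** The strongest reply is that little depends on this rule. It governs a sensitivity analysis, the primary model is fixed without reference to baseline tests, and the main protocol lists the cognitive outcomes as exploratory. All of that stands and limits the weight of the point.

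A reader might infer that the rule costs the trial power that adjustment for known predictors would recover. The documents do not support that for stage 1. The treatment effect is the Group x Time term, and pre-specified main effects would gain no more there than selected ones (step 3). A power gain needs a covariate that predicts 16-week change, or a different model, and the documents give no such correlation.

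A reader might also infer that agreement or disagreement with the primary analysis would vary at random with the variables selected. With complete data in stage 1 it would not, because agreement is built in.

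Three further objections have force.
- The 5% threshold is not the plan's. If false discovery rate control covered the baseline tests, the chance of any selection under randomisation would be about 5%, not 40% to 64%.
- Chance is the full explanation only at the first randomisation. By stage 2, differences between HIIT and CME may also reflect dropout.
- The section Cognitive Function analyses composites both with and without demographic correction. Where the correction covers age, sex or education, those covariates have less left to explain.

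It can also be said that adjustment appears elsewhere: relevant baseline covariates are mentioned, and sex and race interactions are planned. The former are unnamed and tied to missing data, and the latter are exploratory moderation analyses. Neither supplies a pre-specified adjusted check.

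**Conclusion.** The point holds as a minor, inexpensive improvement. The plan states twice that baseline differences decide the covariates, and that criterion is unrelated to prognosis at the first randomisation. The 40%, 54% and 64% figures rest on an assumed 5% threshold and on 10, 15 or 20 independent variables.

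The primary cognitive analysis is unaffected and there is no type I error inflation. The more practical weakness is that, in stage 1 with complete data, main-effect adjustment cannot change the result, so agreement says nothing about robustness. With 20% dropout it can move the estimate only slightly.

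Replacing the selection rule alone would not cure this; the way the covariates enter must also be stated. Any gain in precision depends on how well they predict the analysed outcome. Under the assumptions above it runs from none to about 8% of the SE for a 4-month ANCOVA. For a stage 2 group main effect with R² 0.3 it is about 19% (0.176 to 0.143). Gains would be smaller for demographically corrected composites.

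**What to change.** Delete both sentences of the baseline-test rule. In their place, pre-specify one adjusted sensitivity analysis with a fixed set kept whatever the observed balance: site (already in the model), sex and age category (the stratification factors), and education. The Cognitive Substudy Aims already list education as a predictor, though of activity maintenance.

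State how the set enters:
- Stage 1: covariate x Time terms, or a 4-month ANCOVA on the baseline cognitive score.
- Stage 2: main effects where the model is reduced to group main effects.

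Report baseline characteristics descriptively, without using tests to choose covariates.

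The cost is a few sentences in the analysis plan and a few degrees of freedom. No new data are needed.

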## COGNITIVE SUBSTUDY

Newly enrolled participants at UW/UCD sites will have the option to enroll in the cognitive substudy, which per the Timeline table above, will include cognitive assessments at current study visits (baseline, 16 weeks and 28 weeks) and a new 48 week visit which will include cognitive assessment, blood draw, and psychological mechanisms of adherence measures (which includes text messaging surveys and traditional paper pencil questionnaires). Further detail below. All enrolled UAB site participants will receive these assessments.

**Cognitive Function** will be assessed using a gold-standard battery from the National Alzheimer's Coordinating Center (NACC) Universal Data Set (UDS), which balances participant burden with acquiring a comprehensive assessment. The assessment will be conducted by staff who are blind to intervention group. Staff will be trained and certified by the study PI and will be supervised weekly via meetings and communication. 30% of batteries will undergo double scoring by another staff member and 10% of batteries will be triple scored by the study PI. The PI will also observe assessments quarterly (either in person or video).

We will examine several outcomes, including continuous composites (corrected and uncorrected for demographics) across each domain, as well as a global cognitive functioning composite. We will also examine self-reported cognitive symptoms and declines in daily function. Finally, we will use cognitive T scores and subjective symptoms and everyday functioning declines to generate cognitive diagnoses. Though there are many approaches to operationalizing cognitive impairment in HIV, and in MCI, exist, we will employ validated approaches that are consistently used in neuroAIDS. Despite subtle differences in definitions, most include mild impairment in cognitive function (e.g., ~1 SD below mean on 2 tests/domains), and evidence of either subjective cognitive deficits or declines in daily function.

| One-hour Neurocognitive Assessment Battery |  |
|--|--|
| Domain                                     | Measure  |
| Depression and Everyday Functioning        | Depression: Patient Health Questionnaire 9-item Depression; Everyday Function & Cognitive Symptoms: Functional Activities Questionnaire, Cognitive Failures Questionnaire;   |

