For exploratory analysis, sex-by-group interaction and/or race-by-group interaction will be included in above models to explore the potentially moderating effects, conducted according to the rigorous methods proposed by Hayes. Given significant treatment effects on cognitive function, a PATH analysis will be conducted to explore the potential mediation effects of biomarker changes on cognitive function. We will also examine whether changes in parent R01 outcomes (e.g., VO2, physical function, fatigue) mediate cognitive changes. The exploratory blood markers will be obtained at baseline, 4- and 12 months, while the MRI neuroimaging markers will be obtained at the UAB site at baseline and 4 months. The group difference of biomarkers will be evaluated using a similar linear mixed regression model:  $\text{scores} = \text{Group} + \text{Time} + \text{Group} \times \text{Time}$ , where the group difference on slopes and mean changes will be contrasted.

Our secondary aim is to examine psychological MoA of adherence to habitual PA at 12 months. We will examine distal predictors (i.e., sociodemographics, physical health, intervention type [HIIT vs CME and coaching vs control], changes in parent R01 outcomes [e.g., weight loss, physical function, fatigue] using laboratory and survey data, and proximal psychological predictors using EMA (e.g., self-efficacy, perceived benefits, motivation, social support). First, we will use a linear mixed regression with random intercept:  $\text{PA} = \text{Predictor} + \text{Time} + \text{Predictor} \times \text{Time} + \text{Site}$ , to examine the association between PA adherence and each of the predictors of interest, adjusting for study site. Secondly, we will conduct a multiple linear mixed regression with random intercept and all significant predictors detected above as fixed effects to examine the covariate-adjusted association between PA and predictors:  $\text{PA} = \text{Time} + \text{Predictor1} + \text{Predictor2} + \dots + \text{Site}$ . The time-by-predictor interactions will be evaluated and removed from the model if not significant. The variance-covariance structure (e.g., AR1) in above models will be determined by the best model fit measured by Bayesian information criterion (BIC).

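### The cognitive substudy's stage 1 model does not adjust for the baseline score, so its test is a change-score comparison: valid, but less precise than the data allow

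*Combined protocol and SAP*

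**What the plan says.** Under Cognitive Substudy Statistical Analysis, stage 1 covers baseline to 4 months and uses "a general linear mixed model with participant ID as random effect", with fixed effects Group, Time, Group × Time and Site. The interaction is read as the treatment effect: "The significant interaction term in above model indicates a significant difference between two trajectories/slopes, i.e., treatment effect". A companion analysis follows: "The group comparison on the mean changes will also be contrasted with t test for effect size".

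Baseline information enters in two other places. Missing data are to be mitigated by "mixed effects modeling with baseline covariates that are conceptually relevant and associated to consistency in data collection"; these covariates are not named, and the baseline score is not among the terms of the stage 1 model. Variables found to differ between groups at baseline are added in a sensitivity analysis.

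For the biomarkers, "The group difference of biomarkers will be evaluated using a similar linear mixed regression model". Blood markers are taken at baseline, 4 and 12 months; neuroimaging at baseline and 4 months only.

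Allocation is 1:1. The Exercise Intervention paragraph of section D says the site-specific procedures "use permuted blocks with stratification by sex and 10-year age categories". Sex and age category are not in the stage 1 model.

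**The concern.** In a randomised comparison, a score measured before allocation has the same expected value in both arms. A model that still estimates a separate baseline difference uses information on a quantity that the design already fixes. The baseline score then sits in the outcome vector but does not reduce the residual variance of the 4-month comparison as it would in an ANCOVA.

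What is at stake is precision on the substudy's primary aim. The substudy plans 110 participants (Study Timeline), states no power, and spreads its tests over several outcomes under false discovery rate control. Any chance baseline difference between arms also passes into the estimate through regression to the mean.

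**Working it through.** **Inputs.** N = 110 (Study Timeline). Two-sided tests (Cognitive Substudy Statistical Analysis). A 0.05 level and 20% dropout are stated for the parent trial (section F, Sample Size Calculations) and are assumed here. The same paragraph uses ρ = 0.7 or 0.5 for walk time, fatigue and respiration. No ρ, SD, effect or power is given for any cognitive score, so ρ from 0.5 to 0.9 is an assumption.

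**1. The plan's own practice.** There is no cognitive figure to reproduce. For State 3 respiration the change SD is 180 × √(2(1 − 0.5)) = 180, the difference is (50% − 30%) × 580 = 116, and 40 per group gives 81.2% power, matching the stated >81%. The document therefore sizes that outcome on the raw change score.

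**2. What the stage 1 test is.** With both visits observed, the random-intercept interaction equals the difference in mean change. In simulated complete data (N = 110, three sites, ρ = 0.5 and 0.7) the largest discrepancy was 0.0. With 20% dropout the identity no longer holds, because people with only a baseline visit contribute; single estimates then differed by up to 0.17 SD at ρ = 0.5.

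**3. Efficiency, equal variances.**
- Change score: variance proportional to 2(1 − ρ).
- Baseline-adjusted: proportional to 1 − ρ².
- Ratio: (1 − ρ²) / [2(1 − ρ)] = (1 + ρ)/2, so the loss is (1 − ρ)/2.
- With a share d seen only at baseline: loss = (1 − ρ)² / [(1 − ρ²)/(1 − d) + (1 − ρ)²]. At ρ = 0.5 and d = 0.2 this is 0.25 / (0.9375 + 0.25) = 21%.

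**4. Power.** 110/2 × 0.8 = 44 completers per arm. Take the effect that the change-score test detects with 80% power and recompute with the adjusted variance.

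| Assumed ρ | Variance loss, complete data | Same, standard-error scale | Variance loss, 20% baseline-only dropout | Power instead of 80% (44 completers per arm) |
|---|---|---|---|---|
| 0.5 | 25% | 13.4% | 21% | 90% |
| 0.6 | 20% | 10.6% | 17% | 88% |
| 0.7 | 15% | 7.8% | 12% | 86% |
| 0.8 | 10% | 5.1% | 8% | 84% |
| 0.9 | 5% | 2.5% | 4% | 82% |

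An exact generalised least squares calculation with 54 per arm and three sites gives the same complete-data losses.

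**5. Unequal variances.** If the 4-month SD is 0.9 times the baseline SD, the loss for ρ = 0.5 to 0.7 is 33% to 25%; at 1.1 times it is 18% to 8%.

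**6. Whether the sensitivity analysis closes the gap.** Adding a baseline variable as a main effect, even the baseline score itself, to the random-intercept model leaves the interaction unchanged with complete data, because the interaction is a within-person contrast. That analysis would return the primary estimate.

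**7. Chance imbalance.** The change-score estimate moves by −(1 − ρ) per unit of observed baseline difference. One standard error of that difference at 44 per arm is √(2/44) = 0.21 SD, which shifts the estimate by 0.11 SD at ρ = 0.5, 0.06 at 0.7 and 0.04 at 0.8.

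**The case against.** **The planned test is valid.** It is unbiased under randomisation, keeps its type I error, and its standard error already reflects chance imbalance. This stands: the point is about efficiency. Cognition is also listed among the exploratory outcomes of the whole trial, although it is primary within the substudy.

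**A reader might infer a loss of 15% to 25%.** That range follows from ρ = 0.7 and 0.5, which belong to other outcomes and which the plan itself calls conservative. At ρ = 0.8 to 0.9 the loss is 10% to 5%. The figure is an assumption range and not a property of this plan.

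**A reader might infer that the free Group term buys nothing.** The documents do not secure that. Randomisation closes the third baseline visit, the note to Table 3 does not fix the visit for cognitive testing, and the table appears to mark week 0 as well (its column alignment is uncertain). At UW and UCD the substudy is optional and open to anyone in the parent trial, and participants know their arm. If testing or opt-in followed allocation, the expected baselines need not be equal, and a forced common mean could bias the result. This stands, and it sets a precondition for the fix.

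**A reader might infer that deleting Group is enough.** With categorical Time, Time + Group × Time still has four mean parameters, the same model as before. A shared baseline needs three: one baseline mean and one 4-month mean per arm.

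**A reader might carry the figures to all biomarkers.** Blood markers have three time points, so the two-time-point identity does not apply to them.

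**Conclusion.** The concern holds as one of efficiency. With complete data, stage 1 is a raw change-score comparison, and neither the unnamed baseline covariates nor the planned sensitivity analysis supplies baseline-score adjustment. The variance-scale loss is (1 − ρ)/2 under equal variances. Over an assumed ρ of 0.5 to 0.9 that is 25% to 5% with complete data, or about 21% to 4% with 20% baseline-only dropout. The matching power gain is from 80% to between 90% and 82%. The size depends on a correlation that the plan does not give, and at high ρ it is small. A shared baseline mean is justified only if the cognitive baseline and opt-in precede allocation. The finding does not make the planned analysis invalid or biased.

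**What to change.** In Cognitive Substudy Statistical Analysis:

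1. State that the cognitive baseline test and substudy opt-in take place before randomisation. Where that cannot be said of some participants, the shared-baseline assumption does not cover them, and the free-baseline model should be reported alongside.
2. Make the primary stage 1 analysis one of these:
   - ANCOVA of the 4-month score on baseline score, site, sex and age category. It uses only participants with both visits.
   - A constrained mixed model with one shared baseline mean, categorical time, an explicit treatment-by-4-month indicator set to zero at baseline in both arms, site, sex and age category, and an unstructured 2 × 2 covariance. It keeps participants with a single visit.
3. Report the adjusted 4-month contrast in place of the t test on change.
4. Use the same form for the neuroimaging markers. For blood markers, constrain the baseline mean and report contrasts by visit.

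The analysis change is SAP wording only: baseline scores and randomisation strata are already collected, and no participants or visits are added. The timing statement needs a check of when cognitive testing and opt-in actually occur at each site.
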